36 (±2 weeks) weeks Androgen Deprivation Treatment (may start treatment before consenting to study) (may join study at any point of 36 weeks of treatment or at the end of treatment if PSA has normalized)

PSA Normalizes Start Radiation to all known sites of disease (if joining study after start of Androgen Deprivation Treatment, may start Radiation at the same time, if PSA normalized) (may join study after completion of 36 weeks of treatment and receive Radiation if Serum Testosterone remains at castrated levels)

End Androgen Deprivation Treatment when a total of 36 weeks of Treatment has been received

Follow until PSA Relapse Off Study Restart Androgen Deprivation Treatment Long term followup of patients: PSA, Local Control of stage IV disease, PFS, OS, site and number of new metastases, systemic treatments, long term toxicity.

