5.0 ELIGIBILITY CRITERIA

5.1 Inclusion Criteria

- 5.1.1 Patients with histologically proven diagnosis of adenocarcinoma of the prostate stage N1, N2, N3, M1a, M1b, M1c with \leq 5 metastatic lesions. If the diagnosis of metastasis in the lymph node is based solely on imaging CT scan or MRI, the longitudinal diameter of the lymph node has to be \geq 2.0 cm. If the lymph node is positive on PET or Prostascint scan, the longitudinal diameter of the lymph node on CT scan or MRI has to be \geq 1.5 cm.
- 5.1.2 Patients who have measurable disease must have had X-rays, scans or physical examination used for tumor measurement completed within 28 days prior to registration. Patients must have non-measurable disease assessed within 42 days prior to registration.
- 5.1.3 Patients must have had documented PSA level of > 2 prior to onset of androgen deprivation.
- 5.1.4 Patients might have received up to 36 weeks of adjuvant androgen deprivation therapy and up to 36 weeks of androgen deprivation therapy for metastatic disease prior to enrollment to this study. Patients may be on androgen deprivation for metastatic disease at the time of enrollment to the protocol. Adjuvant therapy must have been completed at least 2 years before

androgen deprivation for metastatic disease and patients must remain hormone sensitive.

- 5.1.5 Prior radiation therapy for metastatic disease is not allowed.
- 5.1.6 Prior chemotherapy for metastatic disease is not allowed. Prior neoadjuvant and adjuvant chemotherapy is allowed. Patients must have recovered from all acute side-effects related to previous systemic therapy.
- 5.1.7 Patients are allowed to receive one prior systemic non-chemotherapeutic treatment (i.e. immunotherapy, receptor tyrosine kinase inhibitor, antiangiogenic agent, differentiating agent) for recurrent or metastatic disease. Patients must have recovered from all acute side-effects related to previous systemic therapy.
- 5.1.8 Use of bisphosphonates is allowed at the discretion of treating physician
- 5.1.9 Patients must be at least 18 years of age.
- 5.1.10 Patient must be capable of understanding the nature of the trial and must give written informed consent.
- 5.1.11 Patients must have a WHO Performance status of 0, 1, or 2.
- 5.2 Exclusion Criteria
 - 5.2.1 Patients with unstable or severe intercurrent medical conditions or active, uncontrolled infection.
 - 5.2.2 Patients with history of orchiectomy.

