6.0 TREATMENT PLAN

Treatment will be given according to the Schema described in section 6.1. A treatment may be stopped for up to 4 weeks to allow for recovery from toxicities. Patients unable to safely resume treatment at that point will be taken off study. 12 weeks constitutes one cycle of hormone therapy.

6.1 Treatment schedule:

- 6.1.1 Patients will begin radiation therapy only after they have demonstrated evidence of PSA normalization after initiation of androgen deprivation therapy (stable or declining PSA level of \leq 4 (or stable or declining PSA \leq pre-treatment level whichever is smaller) on two consecutive measurements. Patients who do not meet these criteria will be taken off protocol.
- 6.1.2 Patients will be divided into two strata:

Stratum 1:

a) Patients who are not on androgen deprivation therapy at the time of enrollment to the protocol will begin androgen deprivation and start radiation therapy after PSA normalization (see section 6.1.1)

b) Patients who are already treated with androgen deprivation therapy at the time of enrollment to the protocol (see 5.1.4) will continue androgen deprivation therapy and begin radiation after meeting criteria for PSA normalization (see section 6.1.1). Radiation therapy will be finished before 36 weeks (± 2 weeks) of hormone therapy is completed.

Stratum 2:

Patients who are enrolled on the protocol towards the end (or after completion) of 36 weeks (\pm 2 weeks) of androgen deprivation so radiation treatment cannot be finished before the completion of 36 weeks of androgen deprivation therapy can still initiate and/or complete radiation therapy as long as their serum testosterone level remains at the castrated levels (<50 ng/dL) and they meet the criteria for PSA normalization (section 6.1.1). Patients will not receive more than 36 weeks of androgen deprivation therapy.

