- 9.2.8 PSA relapse after completion of initial 36 weeks of androgen deprivation therapy is defined as an increase in PSA value to above pre-therapy level or > 10 (whichever is smaller). For example patient with pre-treatment PSA level of 40 will resume androgen deprivation therapy when PSA level is > 10, patient with pre-treatment PSA level of 3 will resume androgen deprivation therapy when PSA level is > 3.
- 9.3 Best Response: This is calculated from the sequence of objective statuses
 - a) CR: Two or more objective statuses of CR a minimum of four weeks apart documented before progression or symptomatic deterioration.
 - b) PR: Two or more objective statuses of PR or better a minimum of four weeks apart documented before progression or symptomatic deterioration, but not qualifying as CR.
 - c) Unconfirmed CR: One objective status of CR documented before progression or symptomatic deterioration but not qualifying as CR or PR.
 - d) Unconfirmed PR: One objective status of PR documented before progression or symptomatic deterioration but not qualifying as CR, PR or unconfirmed CR.
 - e) Stable/no response: At least one objective status of stable/no response documented at least six weeks after registration and before progression or symptomatic deterioration, but not qualifying as anything else above.
 - f) Increasing disease: Objective status of progression or symptomatic deterioration within twelve weeks of registration, not qualifying as anything else above.
 - g) Inadequate assessment, response unknown: Progression or symptomatic deterioration greater than twelve weeks after registration and no other response category applies.
- 9.4 Time-Related Endpoint Definitions
 - 9.4.1 Survival: Defined as the time from registration to time of death due to any cause. If a patient is not known to have died, survival time is censored at the time of last follow-up.
 - 9.4.2 Progression-free survival: Defined as the time from registration to the first observation of disease progression (as defined in 9.2.5) or death due to any cause. If a patient has not progressed or died, progression-free survival is censored at the time of last follow-up.
 - 9.4.3 Time to treatment failure: Defined as the time from registration to the first observation of disease progression, death due to any cause, or early discontinuation of treatment. If failure has not occurred, failure time is censored at the time of last follow-up.

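### PFS, OS and time to treatment failure start at a registration date that may fall before, during or after the 36 weeks of androgen deprivation, so a pooled PFS curve depends on the entry mix

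*Combined protocol and SAP*

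**What the plan says.** Three time-related endpoints share one origin. Section 9.4.1 has "Survival: Defined as the time from registration to time of death due to any cause", 9.4.2 has "Progression-free survival: Defined as the time from registration to the first observation of disease progression" (or death), and 9.4.3 has "Time to treatment failure: Defined as the time from registration to the first observation of disease progression, death due to any cause" (or stopping treatment early).

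Registration is not tied to a point in treatment:
- Stratum 1a (6.1.2): "Patients who are not on androgen deprivation therapy at the time of enrollment to the protocol will begin androgen deprivation".
- During treatment: 5.1.4 allows "up to 36 weeks of androgen deprivation therapy for metastatic disease prior to enrollment to this study", and the schema says that patients "may join study at any point of 36 weeks of treatment or at the end of treatment if PSA has normalized".
- Afterwards: the schema adds that they "may join study after completion of 36 weeks of treatment and receive Radiation if Serum Testosterone remains at castrated levels", and Stratum 2 in 6.1.2 covers "Patients who are enrolled on the protocol towards the end (or after completion) of 36 weeks".

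Section 9.2.5 restricts progression to events that occur while androgen deprivation is being given. Section 5.2.5 excludes men who have already become refractory on an LHRH agonist. Section 10.1 plans Kaplan-Meier estimates of time to progression and overall survival. It mentions neither delayed entry nor the androgen deprivation already received. Only the primary endpoint (9.4.4) has a treatment-based origin: the last bicalutamide dose or the last day of radiation, whichever is later.

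**The concern.** A time-to-event curve is easiest to read when time zero means the same thing for everyone in it. Here time zero is the first day of hormone treatment for one man, the middle of it for another, and some point after its end for a third. The men who register late are also those who have not yet failed on hormones.

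Objective 5 names PFS and OS, and Section 10.0 speaks of an early estimate of effect based on survival. In a single-arm trial of 28 patients these curves will be read as a description of the regimen. If their level is set partly by how many men enrolled early or late, they describe recruitment as much as treatment.

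**Working it through.** **1. The plan's own figure.** Section 10.0 states 83% power for a median time to PSA relapse of 16 against 9 months, with 28 patients, one-sided 0.05, accrual A = 24 months and follow-up F = 12 months. With λ = ln 2 / median, P(event) = 1 − [exp(−λF) − exp(−λ(A+F))]/(λA). This is 0.819 at 9 months and 0.630 at 16 months, or 22.9 and 17.6 expected events. Power = Φ((ln(16/9) − 1.645/√22.9) × √17.6) = 83.5%, which reproduces the stated value. The origin of this endpoint is in 9.4.4 and is not registration, so nothing below changes it.

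**2. Entry screen against event definition.**

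| Element | Refractoriness, 5.2.5 | Progression, 9.2.5 |
|---|---|---|
| PSA | up 25% over baseline, to above 2, on two consecutive values | up 25% over baseline, to above 2 |
| Measurable disease | sum of diameters up 20% | the same |
| Non-measurable disease | clear worsening | the same |
| Lesions | reappearance, or a new lesion | reappearance, or a new lesion or site |
| Failure to return because of death or deterioration | not listed | counted |

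A man who registers late has therefore been selected for not having had what is nearly the PFS event.

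**3. Progression window after registration.** On protocol, androgen deprivation ends at 36 weeks (± 2). A man who registers at treatment week t has a remaining window w = 36 − t weeks, and w = 0 for entry at or after week 36. For example, ten weeks after registration a Stratum 1a patient is in treatment week 10 and can progress. A man who registered at week 30 is four weeks past the end and cannot, yet both sit in the same risk set.

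**4. Illustrative size.** The plan gives no on-treatment progression rate for these patients. I assume a constant rate with a median m of 14 to 30 months. That range is the one in Section 2.1, used here only to set a scale. In weeks (× 52.18/12), m is 60.9 to 130.4. P(countable progression) = 1 − 2^(−w/m), ignoring deaths and dropout.

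| Registration at week | Window w (weeks) | m = 14 months | m = 30 months |
|---|---|---|---|
| 0 | 36 | 34% | 17% |
| 12 | 24 | 24% | 12% |
| 24 | 12 | 13% | 6% |
| 36 or later | 0 | 0% | 0% |

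A constant rate has no memory, so these figures show the window effect alone and leave out the selection in step 2.

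**5. Effect of the mix.** The entry mix is not given. Suppose a share q of the 28 enters after week 36 and the rest at week 0. The expected number of countable progressions is 28 × (1 − q) × P(week 0):
- q = 0: 9.4 (m = 14) or 4.9 (m = 30)
- q = 0.5: 4.7 or 2.4
- q = 1: 0 in both cases

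The treatment and the disease are the same in each row; only the enrolment date differs.

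**The case against.** The strongest reply is that the stakes are descriptive. The primary endpoint does not start at registration. Section 10.0 lists the secondary endpoints as PSA response, safety, feasibility and tolerability, and no test or threshold rests on PFS, OS or time to treatment failure. Objective 5 is long-term follow-up, done partly by chart review. All of this stands, and it limits the weight of the point.

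Four stronger readings are tempting, and the documents do not support them.
- That the pooled curves mean nothing. Time from registration is a defined origin, and it counts no time before enrolment.
- That a planned by-strata comparison of OS or PFS is compromised. The by-strata sentence in 10.0 closes the paragraph on time to PSA relapse and most naturally refers to that endpoint. Section 10.1 names only time to progression and OS, and plans no curve for time to treatment failure.
- That the origin spoils a comparison with the 14 to 30 months in Section 2.1. That figure is for continued suppression, whereas here treatment stops at 36 weeks. The plan does not propose the comparison, and moving the origin would not make it valid.
- That one can state a gap in months between strata due to the clock alone. A smooth survival model from the start of androgen deprivation mixes clock shift with selection. With a median near two years it also places most events after week 36, where 9.2.5 no longer counts them. Stratum 1 itself combines untreated men with men already on treatment.

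It can also be said that delayed entry assumes entry time is otherwise unrelated to outcome. Late entrants must have a normalized PSA and remain hormone sensitive, so that assumption is doubtful. This stands as a limit of the remedy. The further claim that re-timing cannot help men who enter after week 36 does not stand. On a clock from the first dose, every patient has the same 0 to 36 week progression window, and those men simply add no time at risk within it.

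**Conclusion.** The point holds as a cheap improvement. A registration-based PFS or time-to-progression curve pools men whose on-protocol progression window runs from 36 weeks to none, after an entry screen that nearly repeats the event definition. It therefore depends on the entry mix and describes no common treatment point. No other section corrects this.

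Under the stated assumptions, the chance of a countable progression goes from 34–17% (entry at week 0) to 0% (entry after week 36). This rests on a constant rate, the assumed medians, and 9.2.5 applied to protocol treatment. Section 9.4.2 does not say whether progression on hormones restarted after PSA relapse, off protocol, would count. If it did, the window for late entrants would not be strictly empty, but windows would still differ by entry time.

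OS is affected less. Death has no such window, so only the shifted origin and the selection remain, and these matter less as survival lengthens. The shift is 36 weeks or somewhat more, because entry after completion is allowed while testosterone stays castrate. The primary endpoint, the 83% power and the sample size of 28 are not affected.

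**What to change.** In 9.4 and 10.1:
1. Report the registration-based PFS or time-to-progression curve and the OS curve by androgen-deprivation status at registration: none, on treatment, completed.
2. Add an analysis timed from the first dose of androgen deprivation for metastatic disease, with each patient entering the risk set at registration (delayed entry).
3. Say in 10.1 whether time to progression means the PFS of 9.4.2, since 9.4 does not define it separately.

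The cost is wording. The start date is already needed to count the 36 weeks. The downside is imprecision: with 28 patients the three groups will be small, and so will the early risk sets under delayed entry. The report should also state that delayed entry takes entry time to be otherwise unrelated to outcome, and that the PSA and hormone-sensitivity requirements make this uncertain. For that reason the re-timed curve should stand beside the split display and not replace it.

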10.0 STATISTICAL CONSIDERATIONS

This is a phase II study to evaluate the efficacy and safety of radiation to metastatic sites plus 36 weeks months of androgen deprivation in patients with hormone-sensitive prostate cancer. The primary endpoint in this trial will be time to PSA relapse as defined in 9.2.8 and 9.4.4. Secondary endpoints include PSA response to treatment, safety, feasibility and tolerability.

Based on the prior data, the median time to PSA relapse (PSAR) following 36 weeks of androgen deprivation therapy, is approximately 40 weeks. This study would then look to detect an improvement beyond 40 weeks. For a one-sample, one-sided, 0.05-level test using the large-sample normal approximation for the distribution of the logarithm of the maximum likelihood estimator of the exponential parameter, with 28 patients and assuming accrual of 24 months and follow-up of 12 months, there will be 83% power for the test of the null hypothesis that the median PSAR is 9 months vs. the alternative that the median PSAR is 16 months as measured from the end of the twelve months of androgen deprivation therapy. If the parametric estimate of median PSAR is 13 months, this would suggest activity for the addition of radiation therapy. The initial analysis will include all patients, although analysis by strata will also be conducted in an exploratory fashion as will the role of previous adjuvant hormone treatment.

In addition to obtaining an early estimate of the effect of this therapy based on survival, feasibility and toxicity will also be carefully monitored in this novel approach.

10.1 Interim analysis for toxicity

With 28 patients, we will be able to estimate the complication rate (any grade 3 or higher toxicity attributable to the radiation or combination of androgen deprivation/ radiation therapy) with a maximum standard error of 19%. If less than 2 cases have radiation induced complications, we can rule out a 17% complication rate or higher with 95% confidence. Since this therapy is not expected to cause severe toxicities, if at any time more than 25% of the patients experience a radiation induced complication, the study will be halted pending review.

The outcome status (in terms of toxicity, response, reason off study, progression, and survival) of all eligible patients who are registered will be reported. All patients who receive any treatment will be included in the summaries of toxicities. The CTCAE v. 3.0 toxicity criteria will be used. Toxicity information recorded will include the type, severity, time of onset, time of resolution, and the probable association with the study regimen. Time to progression and overall survival will be estimated using the product-limit method of Kaplan and Meier.

The sample-size, as justified above, is 28 patients. With an expected accrual of 14 patients per year, it will take approximately two years to complete the accrual.

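### Section 10.1 gives a maximum standard error of 19% for the complication rate; with 28 patients the maximum is 9.4%, and 19% is about the 95% half-width

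*Combined protocol and SAP*

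**What the plan says.** Section 10.1 (Interim analysis for toxicity) opens with the precision available for the complication rate: "With 28 patients, we will be able to estimate the complication rate". It defines a complication as "any grade 3 or higher toxicity attributable to the radiation or combination of androgen deprivation/ radiation therapy", and gives the precision as "androgen deprivation/ radiation therapy) with a maximum standard error of 19" per cent.

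A second precision statement follows: "If less than 2 cases have radiation induced complications, we can rule out a 17% complication rate or higher with 95% confidence". The section then sets a halting threshold of 25% for radiation-induced complications.

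The number of patients is the same throughout. Section 10.1 closes with "The sample-size, as justified above, is 28 patients", and Section 10.0 bases the power calculation on a design "with 28 patients and assuming accrual of 24 months and follow-up of 12 months". On who counts for toxicity, Section 10.1 says: "All patients who receive any treatment will be included in the summaries of toxicities".

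**The concern.** The complication rate is a single proportion: patients with at least one qualifying event, out of patients treated. Once the number of patients is fixed, its largest possible standard error is fixed too and needs no clinical assumption. For 28 patients that value is well below 19%.

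Toxicity is one of the objectives in Section 1.0, and safety is a secondary endpoint in Section 10.0. Of the two precision statements in Section 10.1, this is the general one; the other applies only if fewer than two complications occur. A reader who takes the 19% at face value, or reuses it, would think the toxicity estimate half as precise as it is.

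**Working it through.** **Inputs, all from the document**

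- Patients: n = 28 (Sections 10.0 and 10.1).
- Quantity: one binomial proportion, the share of patients with a grade 3 or higher attributable toxicity (Section 10.1).
- Stated maximum standard error: 19% (Section 10.1).
- Confidence level used in the same paragraph: 95%.

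**Attempt to reproduce the 19%**

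The standard error is sqrt(p(1 − p)/n), which is largest at p = 0.5:

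sqrt(0.5 × 0.5 / 28) = 0.0945, or 9.4%.

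The stated figure is 0.19 / 0.0945 = 2.01 times this. At lower true rates with n = 28 the standard error is smaller still:

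| True rate | Standard error |
|---|---|
| 5% | 4.1% |
| 10% | 5.7% |
| 25% (the halting threshold) | 8.2% |
| 50% | 9.4% |

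**Other denominators**

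- n − 1 = 27: sqrt(0.25/27) = 9.6%.
- n = 14, the patient count in the DSMB reporting interval (Section 16.0): sqrt(0.25/14) = 13.4%.
- n needed for a maximum of 19%: 0.25 / 0.19² = 6.9, so about 7 patients; sqrt(0.25/7) = 18.9%.

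The document describes no analysis of 7 patients and gives no clustering or design effect that would inflate the standard error.

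**What does give 19%**

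The maximum 95% half-width with n = 28 is:

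- 1.96 × 9.4% = 18.5%;
- 2 × 9.4% = 18.9%;
- 19.4% using the t distribution with 27 degrees of freedom;
- 19.4 points from the exact interval at 14/28, which runs from 30.6% to 69.4%.

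**Size of the misstatement**

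A 19% standard error implies a 95% interval of ±1.96 × 19% = ±37 points, against about ±19.

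The difference also shows at the plan's own 25% threshold. With 28 patients the standard error there is 8.2%, and the approximate 95% interval is 25% ± 16.0%, or 9% to 41%. Scaling down from a 19% maximum gives 0.19 × sqrt(0.25 × 0.75)/0.5 = 16.5%. The half-width would then be 1.96 × 16.5% = 32 points, and the interval would include zero.

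**Check of the neighbouring statement**

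P(X ≤ 1 | n = 28, p = 0.17) = 0.83^28 + 28 × 0.17 × 0.83^27 = 0.0054 + 0.0311 = 0.037, below 0.05. The exact one-sided 95% upper limit for 1/28 is 15.9%. The 17% statement therefore holds at n = 28 as a one-sided statement.

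**The case against.** The arithmetic is not in dispute; the objections concern weight and wording.

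- **Nothing depends on the figure.** The sample size comes from the time-to-PSA-relapse test, and neither the 17% statement nor the 25% halting rule uses the 19%. The error is conservative, and any standard error reported at the end would be computed from the data. All of this stands. It limits the consequence but does not make the sentence correct.
- **The worst case is remote.** The maximum occurs at a true rate of 50%, while the plan expects few severe toxicities and would halt above 25%. This is fair, but the plan chose to quote a maximum, and the maximum it quotes is twice the true one.
- **19% is still an upper bound.** The standard error indeed never exceeds 19%. But a stated maximum ordinarily means the largest attainable value, and with n fixed that is 9.4%.
- **The cause is inferred.** The document shows no derivation, so a mislabelled half-width is only the likely origin. This stands, and the conclusion does not rest on it.
- **Fewer than 28 may receive radiation.** Under Section 6.1.1, patients without PSA normalization leave the protocol before radiation. With 20 patients, taken only as an illustration, the maximum would be sqrt(0.25/20) = 11.2%, still far from 19%.
- **The neighbouring rules should not be endorsed in passing.** This also stands. The document does not say whether its 95% is one-sided or two-sided, and the two-sided exact upper limit for 1/28 is 18.3%, above 17%. The halting rule was not evaluated here. The claim is only that neither depends on the 19%.

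**Conclusion.** The concern holds. The largest standard error attainable with 28 patients is 9.4%; the 19% in Section 10.1 is 2.01 times too large and agrees with a 95% half-width (18.5% to 19.4%, depending on the method). The result assumes only a simple binomial proportion in 28 patients, which is how Section 10.1 describes the quantity.

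This is an error in a stated precision figure, not a flaw in the design. It should be corrected because it is wrong by a factor of two in the statistical section.

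**What to change.** In Section 10.1, replace the stated precision with: a maximum standard error of 9.4% (95% confidence interval half-width at most about 19 percentage points). Giving both figures with their labels keeps the 19% where it appears to belong and avoids a second misreading.

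The cost is one corrected phrase. The sample size, the 17% statement and the 25% halting rule are unaffected by this correction, and no analysis or monitoring step changes.
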